2.4 SITE POOLABILITY

Baseline demographic data (age, gender, race and contact lens wear) and baseline iDesign refractions (IDS, IDC and IDSE) will be reported by site. To assess the poolability of the sites based on baseline variables, a one-way ANOVA will be used for continuous variables and the Chi-square test or Fisher's Exact test will be used for categorical variables.

For the key primary effectiveness endpoints, data will also be reported by site. A logistic regression analysis will be used to evaluate the effect of significant demographic and baseline factors on the key primary effectiveness endpoints while controlling for site. An alpha level of 0.15 will be used to assess the site poolability.

3 ACCOUNTABILITY/DEMOGRAPHICS AND PREOPERATIVE REFRACTIONS

3.1 ACCOUNTABILITY

Subject accountability will be summarized as a frequency distribution by scheduled visits. The frequency and proportion of available eyes, including those outside of the interval, and the frequency and proportion of missing eyes (forms not yet received, active, missed visit, lost to follow-up or discontinued) will be reported.

3.2 DEMOGRAPHICS

Subject demographic data will be subject-based. Age will be summarized with descriptive statistics with mean, standard deviation, minimum and maximum. The frequency distributions of sex, race, and contact lens history will also be tabulated. The demographic data will also be reported by site.

3.3 PREOPERATIVE REFRACTIONS

Preoperative refractions including iDesign refractions (IDSE, IDS and IDC) and manifest refractions (MRSE, MRS and MRC) will be reported. Preoperative IDSE and IDS by preoperative IDC will be tabulated by each dioptric bin. The frequency and proportion of eyes in each dioptric bin will be reported.

4 INTRAOPERATIVE PARAMETERS

Intraoperative findings will be reported and include the percentages of eyes with operative complications, the use of iris registration during treatment, and any other reported incidents.

5 POSTOPERATIVE ANALYSES – PRIMARY ENDPOINTS

Primary effectiveness and safety endpoints will be evaluated at the stability time-point.

5.1 PRIMARY EFFECTIVENESS ENDPOINTS

Monocular UCVA

The frequency, proportion and 95% confidence interval of the proportion of eyes with each acuity line of UCVA (20/16 or better, 20/20 or better, 20/25 or better, 20/40 or better, 20/100 or better and worse than 20/100) will be summarized over time.

The success criterion is the proportion of eyes achieving the target of 20/40 or better is at least 85%.

MRSE Predictability (within 0.50 D and 1.00 D of Target)

Summary statistics (mean, standard deviation, median, minimum and maximum) will be reported over time for MRSE.

18NOV2015/3.0

For this study, the attempted MRSE is emmetropia and therefore is calculated as "– Preop MRSE". The achieved MRSE is defined as "Postop MRSE – Preop MRSE". Eyes that are under-corrected will have a residual MRSE <0.00 D (e.g., myopic eyes that are under-corrected by more than 1.00 D will have a postoperative MRSE < -1.00 D). Eyes that are over-corrected will have a residual MRSE >0.00 D (e.g., myopic eyes that are over-corrected by more than 1.00D will have a postoperative MRSE < -1.00 D).

The frequency, proportion and 95% confidence intervals of eyes with achieved MRSE within 0.50 D and 1.00 D of attempted MRSE will be summarized over time. The frequency and proportion of eyes under-corrected MRSE by more than 1.00 D or 2.00 D and eyes over-corrected MRSE by more than 1.00 D or 2.00 D and eyes over-corrected MRSE by more than 1.00 D or 2.00 D will also be summarized over time.

The success criterion for MRSE predictability within 0.50 D is that the proportion of eyes with MRSE within 0.50 D at the stability time-point is at least 50%. In addition, the success criterion for MRSE predictability within 1.00 D is proportion of eyes with MRSE within 1.00 D at the stability time-point is at least 75%.

Refractive Stability

Refractive stability will be evaluated for two cohorts: a "consecutive cohort" (eyes with data at two consecutive visits) and a "consistent cohort" (eyes with data at all periodic visits through the point of stability and the confirmatory time point). The frequency, proportion and 95% confidence intervals of eyes with MRSE and MRC changes ≤ 1.00 D, as well as ≤ 0.50 D, between visits will be reported.

Refractive stability requires at least 95% of the eyes to have a change \leq 1.00 D of MRSE and MRC between refractions performed at 1 month and 3 months after surgery or any two refractions performed at least 3 months apart.

Additionally, the mean change (paired differences) in MRSE and MRC between visits will be calculated to evaluate the additional refractive stability criteria. The mean rate of change in MRSE and MRC should be ≤ 0.50 D per year (≤ 0.04 D/month) to meet the stability requirement. The mean rate of change in MRSE and MRC should decrease monotonically over time. At the point of stability, the 95% confidence intervals of the mean rate of change in MRSE and MRC between visits should include zero. Lastly, stability is to be confirmed at least 3 months after the stability time point by a statistically adequate subgroup using the same refractive stability criteria.

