#### 4. STUDY DESIGN

This study is a 12-month, prospective, multi-center, bilateral, open-label, non-randomized clinical trial.

17NOV2015/ 3.0 7 PR/STAR-115-MIPS

<sup>1 Manche, E. and W. Haw. (2011). Wavefront-Guided Laser in Situ Keratomileusis (Lasik) versus Wavefront-Guided Photorefractive Keratectomy (Prk): A Prospective Randomized Eye-to-Eye Comparison. Trans Am Ophthalmol Soc. 2011 Dec; 109: 201–220

Up to 334 subjects will be enrolled to achieve a minimum of 334 treated eyes (of approximately 167 bilaterally-treated subjects), resulting in at least 300 evaluable eyes at the point of refractive stability. Twenty or more eyes are intended to be treated per dioptric bin across both sphere and cylinder treatment ranges.

The study will be conducted at up to 7 sites in the USA. Each site should enroll a minimum of 20 eyes, and no site may treat more than 25% of eyes.

A distance-corrected contrast sensitivity substudy will also be conducted with at least 65 eyes from a single site.

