#### 6.3 DEFINITION OF THE TIME POINT OF REFRACTIVE STABILITY

The critical time point for analysis of safety and effectiveness is based on achievement of refractive stability. The criteria for determination of the point of refractive stability are as follows (per ANSI Z80.11-2012):

- At least 95% of the treated eyes have a change ≤1.00 D of MRSE and MRC between refractions performed at 1 month and 3 months after surgery or any two refractions performed at least 3 months apart
- The mean rate of change in MRSE and MRC, as determined by a paired analysis, is ≤0.5 D per year (0.04 D/month) over the same time period
- The mean rate of change in MRSE and MRC decreases monotonically over time, with a projected asymptote of zero or a rate of change attributable to normal aging
- The 95% confidence interval for the mean rate of change includes zero or a rate of change attributable to normal aging
- Stability is confirmed at least 3 months after the stability time point by a statistically adequate subgroup.

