2 ANALYSIS POPULATIONS

2.1 ANALYSIS POPULATIONS/HANDLING OF MISSING DATA

The safety population will be the primary analysis population for all endpoints and includes all eyes that receive study treatment. However, if there are greater than 5% of eyes with missing study exams at the stability time point, an intent-to-treat (ITT) population will be used as the primary analysis population for the primary effectiveness endpoints. In this case, missing data will be imputed. For continuous variables, the planned method to use is the MCMC full-data imputation as described in Little & Rubin¹. For data with a binary response and a monotone missing pattern, the planned method is to use the monotone logistic regression multiple imputation method. Data imputation and analysis will be performed using the MI and MIANALYZE procedures² in SAS[®] (Version 9.2).

¹ Little, R. and Rubin, D. Statistical Analysis with Missing Data, John Wiley & Sons, Inc. New York, Second Edition, (2002)

² SAS Institute. The MI and MIANALYZE Procedures. SAS/STAT 9.2 User Guide. and SAS/STAT User Guide for the MI Procedure: Imputation Methods. Cary, N.C.

In addition to the above imputation methods, sensitivity analyses using different imputation approaches will also be performed for primary effectiveness endpoints for the ITT population. A worst-case scenario with the worst score assigned to the missing data will be performed. A tipping point analysis will also be performed.

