For comparisons across categories, a Mantel-Haenszel chi-square test for ordinal data and a Cochran-Mantel-Haenszel test for non-ordinal data will be used to compare the observed percentages across categories. Additionally, the results for each category will be compared to the target criterion for each study endpoint using chi-square goodness-of-fit test. All statistical tests and p-values will be reported as 2-sided and a significance level of 0.15 will be used to assess homogeneity of the primary safety and effectiveness endpoints for baseline and demographic variables.

Statistical significant factors will be further investigated.

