9 SAMPLE SIZE CALCULATIONS

Per ANSI Z80.11-2012, Annex E, the sample size calculation is to be based on the probability of observing an adverse event at a rate greater than or equal to the expected rate but less than or equal to an acceptable target. This study will be powered to detect the percentage of eyes losing 2 or more lines of BSCVA at 3 months. In the approved indication for the original STAR S4 IR System Myopia clinical study (PMA P930016-S016, approved 05/23/03), the percentage of eyes losing 2 or more lines of BSCVA at 3 months was 0.3% (1/318, 95% exact CI (0.00%, 1.7%)). The target rate will be chosen to assure that the proposed study will be able to detect at least the upper limit of the exact 95% confidence interval.

The hypothesis is

$$H_{o}: p_{trt} \leq p_{target}$$

$$H_1$$
: $p_{trt} > p_{target}$

where

 p_{trt} = Estimate of the percentage of eyes losing 2 or more lines of BSCVA at 3 months using the STAR S4 IR and iDesign System

18NOV2015/3.0

p_{target} = Expected percentage of eyes losing 2 or more lines of BSCVA at 3 months per previously approved PMA P930016-S016

Using the binomial distribution with an alpha of 0.05, 80% power and a sample size of n=300 eyes, a rate of at least 1% can be detected. Therefore, a sample size of 300 evaluable eyes at the time point of stability is required.

CONTRAST SENSITIVITY SUBSTUDY SAMPLE SIZE

The sample size calculation for the substudy is based on ANSI guidance (ANSI Z80.11) using noninferiority approach. With a sample size is 65, a paired t-test with a 0.05 one-sided significance level will have over 90% power to detect the paired difference mean contrast sensitivity is no less than 0.15 below zero when the expected mean difference is 0, assuming the non-inferiority margin equals 0.15 and the standard deviation of the difference is 0.40.

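### Pooled eye-level intervals and tests make no allowance for correlation between fellow eyes, so when that correlation is positive the intervals are too narrow and the check that the stability interval includes zero fails too often

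*SAP*

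**What the plan says.** Protocol 4 plans 334 treated eyes from "approximately 167 bilaterally-treated subjects". SAP 2.1 sets the analysis set by eye: "The safety population will be the primary analysis population for all endpoints and includes all eyes that receive study treatment".

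The outputs follow that unit. SAP 5.1 reports "The frequency, proportion and 95% confidence interval of the proportion of eyes with each acuity line of UCVA", and SAP 5.1 and 5.2 do the same for MRSE accuracy, BSCVA and cylinder change. The two stability cohorts are defined by eyes. Appendix I of the SAP has separate Subject and Eye columns and puts the primary endpoints, site poolability and outcome stratification under Eye.

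The stability rule is "At the point of stability, the 95% confidence intervals of the mean rate of change in MRSE and MRC between visits should include zero". Protocol 20.2 has the same rule. Protocol 6.3 is wider: "The 95% confidence interval for the mean rate of change includes zero or a rate of change attributable to normal aging".

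For baseline poolability, SAP 2.4 says "a one-way ANOVA will be used for continuous variables and the Chi-square test" (or Fisher's test) will apply, judged at alpha 0.15. SAP 7 uses Mantel-Haenszel, Cochran-Mantel-Haenszel and goodness-of-fit tests, homogeneity also being judged at 0.15, and adds: "Statistical significant factors will be further investigated". The sample size in SAP 9 is worked out "Using the binomial distribution with an alpha of 0.05, 80% power and a sample size of n=300 eyes".

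Neither document mentions fellow-eye correlation, a design effect, GEE, a mixed model, or a cluster-robust or bootstrap variance. The paired differences in SAP 5.1 are between visits, not between eyes, and the logistic regression in SAP 2.4 controls for site, not subject.

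**The concern.** Two eyes of one person, treated on the same day, are unlikely to be independent. If they are positively correlated, a variance computed as if all eyes were independent is too small for any pooled mean or proportion. Three things follow.

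- **The stability decision.** A too-narrow interval excludes zero too often. Stability fixes when every primary endpoint is read, can be examined at up to four interims, and must be confirmed later by the same criteria. The error makes stability harder to declare. It does not create a premature claim.
- **Poolability and stratification.** Tests on factors that vary between subjects (site, gender, race, age) over-reject and set off needless follow-up. Tests on factors that can differ between fellow eyes, such as cylinder bin or wavefront diameter, can instead be conservative and miss real differences.
- **Reported precision.** The intervals around the UCVA, MRSE, BSCVA and cylinder proportions overstate what the study knows.

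**Working it through.** **Inputs.** 300 evaluable eyes (SAP 1 and 9), about 150 subjects if both eyes are evaluable; 334 eyes in 167 subjects (Protocol 20.6); two-sided 95% intervals (SAP 2.3); alpha 0.15 for poolability and homogeneity (SAP 2.4 and 7). The fellow-eye correlation ρ is not in the documents and need not be equal for all variables; the assumed range is 0.3 to 0.9, with 0.1 shown as a low case.

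**The plan's own figure.** 300/(1 − 0.10) = 333.3, rounded up to 334 eyes, or 167 subjects. It reproduces, and contains no design effect.

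**Pooled estimates.** With two eyes per subject the variance inflates by 1 + ρ. Then:

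- effective n = 300/(1 + ρ)
- false failure of the zero check = 2[1 − Φ(1.96/√(1 + ρ))]; coverage is its complement
- at least one of MRSE and MRC fails, if independent = 1 − coverage²
- half-width at 85% = 1.96·√(0.85·0.15·(1 + ρ)/300)

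| ρ | Effective n | Coverage | False failure, one variable | At least one of two fails | Half-width at 85% (points) |
|---|---|---|---|---|---|
| 0 | 300 | 95.0% | 5.0% | 9.8% | 4.0 |
| 0.1 | 273 | 93.8% | 6.2% | 12.0% | 4.2 |
| 0.3 | 231 | 91.4% | 8.6% | 16.4% | 4.6 |
| 0.5 | 200 | 89.0% | 11.0% | 20.7% | 4.9 |
| 0.9 | 158 | 84.5% | 15.5% | 28.6% | 5.6 |

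A simulation of 20,000 trials of 150 subjects with two eyes each, with no true drift, gave eye-level failure rates of 8.4%, 10.9% and 15.4% at ρ = 0.3, 0.5 and 0.9. Intervals on subject means failed 4.8% to 5.3% of the time at every ρ tried.

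**Effect of the correction when there is drift.** Assume 0.04 D between visits, SD 0.35 D and 150 subjects (20,000 runs). The eye-level check passes 49.7%, 48.9% and 49.3% of the time at ρ = 0.3, 0.5 and 0.9; the subject-level check passes 59.7%, 63.5% and 70.6%.

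**Site ANOVA, no site difference, alpha 0.15.** In large samples with 7 sites the rejection rate is P(χ²₆ > 9.45/(1 + ρ)) = 29.7%, 39.1% and 54.7% at ρ = 0.3, 0.5 and 0.9. Simulation with 167 subjects gives 29.8%, 39.5% and 55.6%; with 5 sites, 27.5%, 34.9% and 47.6%. The documents allow up to 7.

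**Stratification, alpha 0.15.** A two-level between-subject factor rejects at 2[1 − Φ(1.44/√(1 + ρ))] = 20.7%, 24.0% and 29.6%. At the other extreme, a factor that always splits the two eyes of a subject rejects at 2[1 − Φ(1.44/√(1 − ρ))] = 8.5%, 4.2% and under 0.1%.

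**Rare events.** At a true rate of 1%, neither eye of a pair has an event with probability 0.99² + 0.0099ρ. Over 150 pairs the chance of at least one event is 1 − (0.9801 + 0.0099ρ)¹⁵⁰ = 95.1%, 92.3%, 89.6% and 80.9% at ρ = 0, 0.3, 0.5 and 0.9.

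**The case against.** The strongest reply is that no success rule is at risk of a false pass. The UCVA, MRSE, BSCVA, cylinder and adverse-event rules compare observed proportions with targets. The one interval rule errs against the sponsor, at the price of a possibly later reading within follow-up already planned to 12 months, and correcting it makes a stability criterion easier to pass. All of this stands; it limits the consequence, not the fault.

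ρ is unknown, and nothing in the documents supports 0.3 as a floor for between-visit changes in refraction. That also stands: at 0.1 the failure rate is only 6.2%. But the direction holds for any positive ρ, and a cluster-robust method estimates the variance from the data without assuming a value.

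Some figures are illustrations or bounds. SAP Appendix III builds spherical equivalent from cylinder, so MRSE and MRC are not independent; for jointly normal estimates the two-variable column is a ceiling. The drift example is one chosen pair of values, no listed factor always splits fellow eyes, and seeing at least one event is not the power criterion in SAP 9. The failure rates also leave out the normal-aging alternative in Protocol 6.3, which would reduce them where it applies.

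Poolability and stratification are screens at a deliberately liberal alpha. True, but 0.15 is the rate the plan chose, and it would not get it.

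Finally, ANSI Z80.11-2012, the stated source of the stability criteria, is not available here, so whether it presumes a per-eye variance cannot be checked.

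**Conclusion.** The concern holds. Both eyes of about 167 subjects enter the pooled analyses, the named tests assume independent observations, and no allowance for pairing is stated. The SAP names no interval method either, so the sizes assume ordinary eye-level intervals and positive ρ.

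For ρ of 0.3 to 0.9 the intervals are 12% to 27% narrower than they should be (1 − 1/√(1 + ρ)). With zero true drift the stability check fails 9% to 16% of the time per variable instead of 5%, and between 9% and 29% for MRSE and MRC together, depending on how they are related. The site ANOVA at 0.15 rejects about twice to nearly four times as often as intended with 7 sites.

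Point estimates and the pass or fail of the other primary rules do not change. Contrast sensitivity (first eye only, Protocol Appendix N), subject-based demographics, binocular UCVA, and the NEI-RQL and satisfaction tables are not affected. Nor is PRVSQ if it is tabulated by subject as in SAP Appendix I, though SAP 6.12 speaks of eyes.

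This should be fixed, mainly because a decision rule and the reported precision depend on it.

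**What to change.** Add to SAP 2.3, before the first stability interim (90% of treated subjects at 3 months), that all pooled eye-level intervals and tests treat the subject as the cluster. This also covers the vector cylinder, keratometry and aberration intervals in SAP 6 and the logistic regression in SAP 2.4. Name the method for each use:

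- **Proportions and mean rates of change:** cluster-robust (GEE) variance or a subject-level bootstrap, with one named as primary. Cluster-robust variances can be combined in MIANALYZE if the imputed analysis becomes primary.
- **Poolability and stratification:** GEE or Rao-Scott tests.
- **Sparse strata (about 20 eyes per bin):** subject-level bootstrap where GEE may not fit.
- **Zero or near-zero counts, where the bootstrap can also collapse:** add an exact interval per subject (event in any eye), labelled as supplementary and as a different estimand.

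In SAP 9, state that the calculation assumes independent eyes and give the effective n over a range of ρ.

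State openly that the wider interval makes the zero check easier to meet, while the mean-rate limit of 0.04 D/month and the requirement on 95% of eyes still apply. Adopted after stability data have been seen, the same change could look like a rescue.

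The cost is SAP wording and programming. Point estimates, thresholds, enrolment and visits stay as they are. The downsides are somewhat wider reported intervals and an easier stability interval check.

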5.2 PRIMARY SAFETY ENDPOINTS

Maintenance of BSCVA

The frequency, proportion and 95% confidence intervals of eyes with each acuity line of BSCVA (i.e. 20/20 or better, 20/25 or better, 20/40 or better, etc.) will be reported over time. The frequency

and proportion of eyes with BSCVA acuity line changes from preoperative (decreases of >2 lines, =2 lines, =1 line, no change, increases of =1 line, =2 lines and > 2 lines) will be summarized over time.

The success criteria for the endpoints regarding maintenance of BSCVA are achieved if the proportion of eyes with a loss of >2 lines of BSCVA from preoperative is <5%, the proportion of eyes with haze beyond 6 months with a loss > 2 lines of BSCVA is <1%, and the proportion of eyes with BSCVA of 20/20 or better preoperatively and BSCVA 20/40 or worse postoperatively is <1%.

Induced Manifest Refractive Astigmatism

Induced manifest refractive astigmatism is defined as the absolute change in manifest refractive cylinder (MRC) from preoperative. The following formula will be used to determine absolute change in MRC (rounded to the nearest 0.25 increment):

```
Absolute Change in Cylinder = |Preop MRC| - |Postop MRC|
```

The frequency, proportion and 95% confidence intervals of eyes with absolute changes in manifest cylinder from preoperative visit will be summarized in categories (increases of >2.00 D, 2.00 D, 1.75 D, 1.50 D, 1.25 D, 1.00 D, 0.75 D, 0.50 D, 0.25 D, no change, decreases of 0.25 D, 0.50 D, 0.75 D, 1.00 D, 1.25 D, 1.50 D, 1.75 D, 2.00 D, > 2.00 D) at each periodic study visit.

The success criterion is achieved if the proportion of eyes with induced manifest refractive astigmatism of >2.00 D is <5%.

Serious, Device-Related Adverse Events

The frequency and proportion of eyes with serious, device-related adverse events throughout the study will be summarized. The success criterion is achieved if the proportion of eyes with serious, device-related adverse events is <1% cumulatively.

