2.3 DATA CONVENTIONS

Descriptive statistics will typically include sample size (N), mean, standard deviation (SD), median, minimum (Min.), and maximum (Max.) as appropriate for continuous variables. For categorical data, the frequency and proportion will be computed.

For continuous variables, statistical tests assuming normality will generally be used. However, the data will be reviewed to evaluate whether the normality assumption is appropriate. If it is found not to be appropriate, either an appropriate transformation of the data (i.e., logarithmic) may be used or the corresponding non-parametric tests may be used. Deviations from the proposed statistical guidelines will be substantiated by sound statistical rationale.

Unless otherwise indicated, alpha will be set to 0.05 for two-sided statistical testing.

For visual acuity data, ETDRS letter scores will be converted to LogMAR values prior to analysis. In addition, if the test distance used is not the standard test distance for the chart, then visual acuity data will be adjusted for the actual test distance used. Appendix II provides formulas for LogMAR conversion and distance adjustment.

For refractive data, all values will be converted to minus cylinder format and sphere will be adjusted for optical infinity. Formulas used for refractive data conversions are included in Appendix III.

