Induced manifest astigmatism (absolute change in MRC from preop, by 0.25D step increment) – (n, %, 95% Cl of eyes)XSerious device-related AEs (N and % of eyes cumulatively)XOTHER ENDPOINTSContrast sensitivity (photopic without glare at 3, 6, 12 and 18cpd; mesopic with and without glare at 3, 6, 12 and 18cpd) - (change from preop: median, 25 th and 75 th percentiles, 95% Cl of the median, and tabulation of eyes unable to see reference patterns)XBinocular UCVA over time - (n, % and 95%Cl for each acuity line:20/16 or better, 20/20 or better, 20/25 or better, 20/40 or better, 20/100 or better and worse than 20/100)XPostop UCVA vs Preop BSCVA - (n and % of eyes with each line change: decrease > 2 lines, =2 lines, =1 line, no change, increase =1 line, =2 lines, > 2 lines)XMRS vs CRS - Mean of MRS and CRS and paired difference (N, Mean, SD, Min., Max)XManifest Cylinder Analysis – Nonvector and VectorXNonvector – MRC accuracy (n, %, 95% Cl of eyes within±0.5D and within±1.0D; mean and SD of attempted and achieved correction; % achieved)XNonvector – reduction of absolute cylinder (N, mean, min, max by preop MRC categories)Nonvector – absolute shift in axis (n and % of eyes with axis shift
Serious device-related AEs (N and % of eyes cumulatively)XOTHER ENDPOINTS—Contrast sensitivity (photopic without glare at 3, 6, 12 and 18cpd; mesopic with and without glare at 3, 6, 12 and 18cpd) - (change from preop: median, 25th and 75th percentiles, 95% CI of the median, and tabulation of eyes unable to see reference patterns)XBinocular UCVA over time - (n, % and 95%CI for each acuity line:20/16 or better, 20/20 or better, 20/25 or better, 20/40 or better, 20/100 or better and worse than 20/100)XPostop UCVA vs Preop BSCVA - (n and % of eyes with each line change: decrease > 2 lines, = 2 lines, = 1 line, no change, increase = 1 line, =2 lines, > 2 lines)XMRS vs CRS - Mean of MRS and CRS and paired difference (N, Mean, SD, Min., Max)XNonvector - MRC overtime (N, Mean, SD, Min., Max)XNonvector - MRC accuracy (n, %, 95% CI of eyes wthin±0.5D and within±1.0D; mean and SD of attempted and achieved correction; % achieved)XNonvector - reduction of absolute cylinder (N, mean, min, max by preop MRC categories)Image for the for t

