APPENDIX II LOGMAR CONVERSIONS AND LINE CHANGES

LogMAR score for UCVA and BSCVA			
Category	LogMAR		
20/16 or better	≤ -0.06		
20/20 or better	≤ 0.04		
20/25 or better	≤ 0.14		
20/32 or better	≤ 0.24		
20/40 or better	≤ 0.34		
20/50 or better	≤ 0.44		
20/63 or better	≤ 0.54		
20/80 or better	≤ 0.64		
20/100 or better	≤ 0.74		
Worse than 20/100	>0.74		

	VA Line Change			
С	Change (LogMAR Postop VA – LogMar Preop VA)	Category		
	< -0.24	> 2 lines better		
	< -0.14 and ≥ -0.24	2 lines better		
	< -0.04 and ≥ -0.14	1 line better		
	0.00 ± 0.04	Equal		
	> 0.04 and ≤ 0.14	1 line worse		
	> 0.14 and ≤ 0.24	2 lines worse		
	> 0.24	> 2 lines worse		
15/2 0	47			

SAP/ STAR-115-MIPS

Key: " * " = multiplication, " - " = subtraction, " / " = division, " ** " = exponent,

log10 = log in base 10, CRF = Case Report Form

Converting ETDRS Letter Scores to LogMAR values When Using Standard Distance for the Chart:

LogMAR value=((ETDRS Letter score for 20/20) – (letter score on CRF))/50

Far VA: LogMAR value = (40-letter score)/50

Converting ETDRS Letter Scores to LogMAR values When NOT Using Standard Distance for the Chart:

LogMAR value=((ETDRS Letter score for 20/20) – (letter score on CRF))/50

+ (log10(standard distance)-log10(actual distance))

Far VA: LogMAR=(40-letter score)/50+(log10(4)-log10(actual distance in M))

Converting from LogMAR to Snellen and Decimal Equivalent:

Snellen Denominator=20*(10**(LogMAR value))

Decimal VA= 20/(Snellen Denominator)

Example

A subject has a letter score of 24 and a test distance of 33 cm.

Converting to LogMAR:

(40 - 24)/50 + (log10(40)-log10(33))=16/50+ (1.602-1.519)=0.32+.083=0.403 LogMAR

The Snellen Denominator is: $20^{(10^{*}(0.403) = 20^{(2.53)} = 50)}$

Decimal VA = 20/50=0.40

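### The SAP formula for induced astigmatism, a primary safety endpoint, is reversed: as printed it counts large falls in cylinder and can never count an increase

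*SAP*

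**What the plan says.** The protocol (6.1, Safety no. 3, and 20.2) limits induced manifest refractive astigmatism above 2.00 D to fewer than 5% of eyes. It gives no formula.

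SAP 5.2 supplies the definition in four steps:

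- The endpoint: "Induced manifest refractive astigmatism is defined as the absolute change in manifest refractive cylinder (MRC) from preoperative".
- The formula, with results rounded to the nearest 0.25 D: "Absolute Change in Cylinder = |Preop MRC| - |Postop MRC".
- The display: changes "will be summarized in categories (increases of >2.00 D, 2.00 D, 1.75 D" and so on through no change to a matching list of decreases.
- The decision rule: "The success criterion is achieved if the proportion of eyes with induced manifest refractive astigmatism of >2.00 D is <5" percent.

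SAP Appendix I repeats the endpoint without a direction: "Induced manifest astigmatism (absolute change in MRC from preop, by 0.25D step increment". SAP Appendix III covers minus-cylinder notation, the infinity adjustment and spherical equivalent, but not change in cylinder.

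**The concern.** Definition, formula and threshold form one chain, and the formula points the opposite way from the endpoint's name. Preoperative minus postoperative magnitude is positive when cylinder falls, so it measures correction. Putting that quantity into a rule that looks for values above 2.00 D selects the eyes with the largest successful corrections and leaves out every eye made worse.

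This is one of the criteria by which the study declares the procedure safe. Applied literally, the rule could pass a treatment that induces cylinder, or fail one that corrects high cylinder well.

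**Working it through.** The documents give no worked example or planned rate for this endpoint, so there is no stated figure to reproduce. The check evaluates the printed formula directly.

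**1. Example eyes.** Write pre and post for the magnitudes of preoperative and postoperative manifest cylinder.

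| Preop to postop cylinder (D) | True change in magnitude | Printed: pre - post | Counted (>2.00)? | Reversed: post - pre | Counted? |
|---|---|---|---|---|---|
| -3.00 to -0.25 | fall of 2.75 | +2.75 | yes | -2.75 | no |
| -3.50 to -0.25 | fall of 3.25 | +3.25 | yes | -3.25 | no |
| -0.50 to -3.00 | rise of 2.50 | -2.50 | no | +2.50 | yes |
| 0.00 to -2.25 | rise of 2.25 | -2.25 | no | +2.25 | yes |

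**2. General result.** If post > pre, then pre - post < 0, which cannot exceed 2.00. No increase in any eye can count. Separately, if pre is 2.00 D or less, then pre - post is at most 2.00, so such an eye cannot be counted at all, whatever happens to it.

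A grid of magnitudes from 0 to 8.00 D in 0.25 D steps confirms this. None of the 300 pairs with a true rise above 2.00 D is counted. Of the 136 pairs with a preoperative value up to 4.00 D and a fall, 36 are counted.

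**3. The SAP's own conventions treat this order as correction.**

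- SAP 2.3 says that "all values will be converted to minus cylinder format", so MRC is zero or negative and pre - post equals postoperative MRC minus preoperative MRC. For the first eye: -0.25 - (-3.00) = +2.75.
- SAP 5.1 uses that same order, "Postop MRSE – Preop MRSE", for the MRSE change it calls achieved.
- SAP 6.5.1 uses preoperative minus postoperative MRC, relative to preoperative MRC, for percent reduction of cylinder.
- SAP Appendix II defines acuity change as "Change (LogMAR Postop VA – LogMar Preop VA" and labels each range better or worse. Cylinder has no such map.

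**4. Does the word 'absolute' rescue it?** With an outer absolute value, -3.00 to -0.25 D and -0.50 to -3.00 D score 2.75 and 2.50, and both count. Corrections would still be counted as harm, and the separate increase and decrease rows would have no meaning.

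**5. Illustration of the literal reading.** Assumptions: the SAP section 7 stratum of iDesign cylinder above 3.00 to 4.00 D is one of the protocol's dioptric bins; it holds the intended 20 eyes (protocol section 4); refractions are in 0.25 D steps; residual cylinder is 0.50 D or less.

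- Inclusion criterion 10 allows at most 0.5 D between manifest and iDesign cylinder, so manifest cylinder exceeds 2.50 D, that is, 2.75 D or more.
- The lowest score is 2.75 - 0.50 = +2.25, so all 20 eyes count.
- This bin alone gives 20/334 = 6.0% of treated eyes, or 20/300 = 6.7% of evaluable eyes. The criterion fails.
- The turning point is 16/334 = 4.8% (pass) against 17/334 = 5.1% (fail), or 14/300 = 4.7% (pass) against 15/300 = 5.0% (fail).
- With 10 such eyes the figure is 10/334 = 3.0%, a pass.

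**The case against.** The strongest reply is that SAP 5.2 corrects itself. The sentence after the formula sorts results in words into increases and decreases, with a separate row for more than 2.00 D on each side. Only the row for increases above 2.00 D fits both 'induced' and the threshold. To reach the wrong answer, an analyst would have to label a fall from 3.00 D to 0.25 D an increase. The protocol criterion has no reversed formula and reads correctly. On this view it is a wording slip with no numerical effect.

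Much of this stands. The intent is plain, and the protocol's background section also speaks of an increase in cylinder when it reports the earlier PRK study. Nothing here shows that the analysis would be done wrongly. The 6.0% figure depends on assumptions about bin size and residual cylinder that the documents do not settle, and it adds nothing to the proof of the reversal.

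What does not stand is that the labels repair the rule. They contradict the formula. A reader reaches the intended count only by overriding the printed equation, and no sentence says that a negative result is an increase or that the 5% limit is read from one row. Text extraction does not explain the reversal either: the bars and minus sign are intact.

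**Conclusion.** The concern holds. The formula as printed measures reduction of cylinder; combined with the limit above 2.00 D, it counts large corrections and no true induction. That part is algebra and needs no assumption.

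The practical size depends on the reading. Under the intended reading the effect is zero. Under the literal reading every induction is missed, and the criterion could fail because of good outcomes; the rate would depend on how many eyes with high cylinder are enrolled and how well they are corrected.

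For scale only, the protocol's background section reports no eye with an increase of 2.00 D or more among 597 treated eyes in the earlier study. The exact 95% upper limit is 1 - 0.025^(1/597) = 0.6%, or 1 - 0.025^(1/397) = 0.9% if based on its 397-eye cohort. That study used a different aberrometer, and these limits treat eyes as independent. They suggest that true increases are rare, not that the definition may stay as it is.

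This is a wrong written rule for a primary safety criterion. It should be fixed, and it is not evidence of a wrong analysis.

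**What to change.** In SAP 5.2:

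- Replace the formula with: change in cylinder magnitude = `|Postop MRC| - |Preop MRC|`.
- State that positive values are increases and negative values are decreases.
- State that only increases above 2.00 D, the first row of the category list, count toward the 5% criterion.
- Drop 'absolute', or define it as change in magnitude, here and in the Appendix I table entry.

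Optionally, add a map from sign to category in Appendix III, as Appendix II already has for visual acuity.

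The cost is one formula line, a sentence or two, and a wording change in Appendix I. No new data are needed, and no sample size or power figure changes.
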